Finally, the systematic review of the literature performed for the development of the national guidelines reveals a lack of evidence for chronic disease models of obesity care rather than models of care that focus on weight loss as the main goal of care (NHMRC, 2013). Chronic disease models of care are of particular relevance to patients with obesity and type 2 diabetes as the likelihood of sustained weight loss in this patient group, even with surgical intervention, has been shown to be low (NHMRC 2013; National Institute for Health and Care Excellence, 2013). It is therefore essential that the secondary complications of obesity (sleep apnoea, hypercholesterolaemia, hypertension, malignancy, infertility, non-alcoholic steatohepatitis, osteoarthritis) (ADIPS 2013; National Cancer Institute 2013; NHMRC, 2013) are identified early and managed effectively in these patients as sustained weight loss is unlikely in spite of weight reduction therapies (NHMRC 2013; National Institute for Health and Care Excellence, 2013).

Study Goals and Objectives

AIM

The aim of this study is to assess the feasibility, acceptability and effectiveness of a rural, multidisciplinary team-based approach to care for adult patients with diabetes mellitus and obesity.

OBJECTIVES OF THIS PROJECT

- To determine if a multidisciplinary multi-intervention clinic for obesity tailored to the individual can reduce absolute cardiovascular and morbidity risk
- To evaluate management and treatment factors as potential predictors of outcome
- To determine whether an interdisciplinary multi-intervention obesity clinic for people with diabetes improves metabolic profile
- To provide process and impact outcomes to substantiate and drive clinical and policy change supportive of a multidisciplinary systematic approach for patients living with obesity

OUTCOMES

Primary Outcome:	change in HbA1c (measured as a continuous variable) in the intervention group compared with the control group
Timepoint:	at 6, 12, 18 and 24 months post baseline; also 6 and 12 months post intervention
Primary Outcome:	change in body weight (measured as a continuous variable) in the intervention group compared with the control group
Timepoint:	at 12 and 24 months post baseline; also 6 and 12 months post intervention
Secondary Outcome:	a decline in Edmonton Obesity status
Timepoint:	at 12 and 24 months post baseline, and 12 months post intervention

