- Once those that met the exclusion criteria were removed this list of potential participants (359) has been ranked from highest to lowest – at this stage they have been allocated a study number of 1 to 359, 1 being the participant with the highest BMI and 359 with the lowest.
- Numbers have been assigned for the two arms of the study from the computer random number generated via excel.
- According to numbers allocated to the potential participant list these are then assigned to the two arms of the study (intervention and control).
- This will occur once ethic approval has been gained and prior to allocation to clinics
- Once case identified and consent gained participants will be recruited from pre-existing clinics
- Outcome measures will be collected at baseline and at appropriate intervals at 6, 12, 18 months and post intervention at 12 and 24 months.

Study Intervention

- Outcome measures including quantitative and qualitative data **not** usually collected as part of a diabetes clinic will be collected to support the development of individualised plans of care:
 - Absolute cardiovascular disease risk

- Patient Health Questionnaire (PHQ-9) [Depression] and Generalised Anxiety Disorder Assessment (GAD-7) [Anxiety] and SF-36 Quality of Life scaling, Assessment and Quality of Life (AQoL), Work Productivity and Activity Impairment (WPAI)
- McCaffery Pain assessment scale and Physical function status
- Edmonton obesity staging
- Sleepiness Scale
- Metabolic clinical markers (HbA1c, lipids, leptin, ketone, vitamin D, B12, TFTs, LFTs, ACR, eGFR)
- Physical measurements (eg BMI, girth, blood pressure)
- Assessment is undertaken initially on the same day by the physiotherapist in terms of pain management and ability to increase physical activity – these assessments are provided to the endocrinologist and Dietitian at which time a treatment plan is developed in partnership with the client by the multidisciplinary team including:
 - Referral to other health professionals and/or assessments (eg Snore Aust, pain clinic)
 - According to scores from psychometric, physical functioning and/or pain scales participants will be divided into groups A, B or C and referred on for either a once off individual consultation, a series of individual consultations or a group program with relevant AHP.
 - Regular psychology review for CBT and other relevant therapies (according to PHQ-9 and GAD-7)
 - Resistance and hydrotherapy training
 - Medical nutritional therapy

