- Following 3 months of lifestyle modification and intensive therapy if weight loss <5% Olistat will be introduced
- At 6 months participants will be referred to self-management program for ongoing behaviour modification
- For relevant cases at 12 months if weight loss not <5% and pathology demonstrates ketosis referral for surgical review
- Bariatric surgical assessment and patient counselling will be provided to determine:
 - whether surgery is indicated;
 - the patient's desire for, and likely tolerance to surgery; and
 - if so, what surgery type is most appropriate for the patient (Nguyen, 2013).

Following the completion of the up to 24 month program (the intervention) participants (both intervention and control) will be invited to continue to be part of the research project by way of providing follow-up data to determine sustainability of the intervention and project. Given Participants are existing patients of the service and will continue to be review as part of routine care at the Diabetes Centre, at their 24 month collection point (intervention and control) participants will be invited to continue with a collection of indicated markers at 6 and 12 months post intervention. If at their last visit (24 months) the participant indicates that they are happy for this to occur this verbal consent will be recorded on the spreadsheet used to collect project data – ie consent given: yes and date. If consent is provided by the participant, ongoing data will be collected following intervention period at 6 and 12 months post intervention.

Intervention Clarified/Differences in two arms of Study TSRAC QUESTION 12 (Response)

- Intervention of interest – **individualised** multidisciplinary multi-intervention assessment and treatment
- The impact of a model of care that assesses, triages and treats **all** factors impacting on metabolic processes from point of entry

Differences in two arms	
Control Group	Intervention Group

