Timing of Assessment Scales TSRAC QUESTION 4 (Response)

- Psychometric and pain measurements will be taken at the same intervals; baseline, 6,12,18,24 months
- Both will be taken on the same day – however, by a different health professional. The only reason for this is that pain assessment falls into a normal assessment for physiotherapists

Orlistat and Other Weight Loss Medication TSRAC QUESTION 10 (Response)

- The use of Orlistat is drawn from recommendations draw from the NICE and NHMRC guidelines for management of obesity.
- Orlistat is currently the only medication registered for use in treating overweight (with comorbidities) and obesity that has been evaluated for long-term safety. Although it is listed on the Repatriation Pharmaceutical Benefits Scheme, it is not listed on the Pharmaceutical Benefits Scheme (PBS). Data suggest that it is more cost-effective in individuals who have numerous comorbidities (type 2 diabetes, hypertension, hypercholesterolaemia)
- Orlistat should be prescribed only as part of an overall plan for managing obesity in adults who hold a BMI of 30.0kg/m² or more (NHMRC 2013).
- The decision to use drug treatment in non- Repatriation clients for longer than 3 months and to a maximum of 6 months (usually for weight maintenance) should be made after discussing potential benefits and limitations with the patient.
- The co-prescribing of orlistat with other drugs aimed at weight reduction is not recommended (NHMRC 2013).
- Other medications found to support weight loss include;

“sibutramine (Horvath et al. 2008), rimonabant (Curioni & André 2006; Nissen et al. 2008; van Gaal et al. 2008), taranabant (Proietto et al. 2010), metformin (Knowler et al. 2009) and

lorcaserin (Smith et al. 2010). However, many of these medications have been associated with adverse effects and have been withdrawn (e.g. sibutramine) or were never approved (e.g. rimonabant, taranabant) in Australia. The evidence on the effects of weight loss medications on health outcomes other than weight loss is limited.” (NHMRC 2013)

[figure not shown]

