 - HbA1c
 - Absolute cardiovascular risk
 - Psychometric measures (PHQ-9, depression and SF-36 Quality of Life)
 - Decline in Edmonton Obesity status (Padwal, 2011)
- Rationale - the power is in general a function of the possible distributions under the alternative hypothesis. As the power increases, the chances of a Type II error occurring decrease. We conducted power calculations to calculate the minimum sample size required using a target variance for an estimate to be derived from the sample eventually obtained.
- We assumed a Cohens d of 0.5 and a power of 0.95 based on estimates in the peer-reviewed literature.
- We assumed significance criteria of 0.05, the probability of the data implying an effect at least as large as the observed effect when the null hypothesis is true must be less than 0.05, for the null hypothesis of no effect to be rejected.
- Further, this assumed:
 - A follow-up period of at least 6 months for each participant.
 - Not all participants will be cared for simultaneously – there will be multiple intakes e.g. as people exit the program enrol new participants and controls.

Analysis TSRAC Q12

- Data will be exported from DiaBASE (Clinical software program) and entered into Excel (Microsoft) for data cleaning, then imported into Stata 12 and SPSS for analysis.
- Analysis will be performed using SPSS and Stata.
- Descriptive statistics will first be calculated to investigate the proportions of categorical variables and the distribution of continuous variables.
- Pearson's chi-square test or Fisher's exact tests will be utilized for investigation of associations between categorical variables, while independent t-tests will be used to investigate differences in continuous data between the control and intervention groups.
- For dichotomous outcomes logistic regression will be performed.
- For continuous outcome data analysis of covariance will be performed to test the effects of predictor variables.
- Adjusted relative risks (aRR) of metabolic and psychometric outcomes will be calculated for the control vs. intervention groups (with 95% confidence intervals) using a Poisson regression model with robust error variance.
- The regression models will include adjustment for age, pre-existing diabetes, socio-economic status and Asian or indigenous ethnicity.

Please provide additional justification on for the effect size with references.

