Physiotherapy

- Involved in planning and development of business processes for access criteria, consent, therapies and data collection
 - Space for assessment and individual or group management
 - Evidence based Assessment protocol including Pain Assessment tool
 - Formulation of Template for Exercise Programme with progression/review capacity
 - Care/Treatment Plan – incorporate data as available for team review
 - Outline group strength/resistance training programme(s) – evidence based
 - Determine validated Outcome Measures – eg. 6 minute walk test; stair climbing test
- Involved in relevant agreed data collection for purposes of reporting and investigating including:
 - Completion of McCaffery Pain assessment scale
 - Completion of a full physical functioning and balance assessment (6 minute walk test (6MWT), Timed Up and Go (TUG), 30-second Chair Stand test (30s-CST)
 - Investigate iPM Clinics structure
 - Utilise ABC – Activity Barcoding Data Collection
 - Providing any relevant information to support progression of 3 monthly progress report as required by vTAHSP.
- Involved in providing Education and Support to the clinic:
 - Collate and share data with the Team for education/research/clinical or funding purposes
 - Utilise data collected to develop presentations for relevant community and professional groups
 - Assist in presenting and/or contribute to presentations of the project to relevant workshops or seminars organised by vTAHSP.
- Involved in the Evaluation and Research activities of the clinic/project:
 - Background searches for evidence on predictors of weight loss associated with physical activity in the obese/diabetic person
 - Support for ongoing trials/research via data sharing , clinical and professional involvement
 - Involved in supporting analysis and interpretation of data

Population Health

- Involved in planning and development of operational business processes for inclusion of self-management programs
- Supports project reporting requirements with advice as relevant (04/15, 10/15, 4/16, 10/16).
- Analysis and interpretation of data (12/2016, 6/2017, 6/2018) to evaluate the model and for the purpose of reports.
- Review of data collection by Population Health - although challenging to draw conclusively from a trial that will last for 12 months and inevitably have a relatively small population, it will be able to “point” to further actions and strategies (0, 12, 24 months).

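### The timing of the two primary outcomes is inconsistent: one schedule bullet conflicts with the outcomes table, and the minimum follow-up and analysis dates fall short of the 24-month visit

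*Protocol*

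**What the plan says.** The Outcomes section names two primary outcomes. HbA1c is assessed "at 6, 12, 18 and 24 months post baseline; also 6 and 12 months post intervention" and body weight "at 12 and 24 months post baseline; also 6 and 12 months post intervention". The table of outcome measures and collection time points has matching columns: baseline, 6, 12, 18 and 24 months, then 6 and 12 months post. It marks HbA1c and the biometric measures, including weight, in every column. The Study Intervention section agrees, with its last two times counted in months after the intervention: "at their 24 month collection point (intervention and control) participants will be invited to continue with a collection of indicated markers at 6 and 12".

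The last bullet of the Randomisation section differs: "Outcome measures will be collected at baseline and at appropriate intervals at 6, 12, 18 months and post intervention at 12 and 24 months".

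Three other places bear on length of follow-up:

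- The sample-size section lists among its assumptions "A follow-up period of at least 6 months for each participant", with several intakes and new people enrolled as others leave the programme.
- Study Duration/Timelines places further recruitment in months 6 to 9 and data analysis and interpretation in months 24 to 26. Data and Safety Monitoring gives the study 2.5 years.
- The Population Health role description contains the remark "although challenging to draw conclusively from a trial that will last for 12 months".

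**The concern.** A protocol should give one answer to the question of when a primary outcome is measured. Here the Randomisation bullet has no visit at 24 months from baseline and none at 6 months post intervention. It adds a visit at 24 months post intervention that appears nowhere else. It also leaves out the 24-month visit at which the Study Intervention section obtains consent for later data.

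The planning assumptions raise a second problem. A minimum follow-up of 6 months ends before the first listed weight outcome. An analysis in months 24 to 26 comes before people recruited in months 6 to 9 can reach their 24-month visit. If the plan ran on those terms, the 24-month comparison would rest on the earlier recruits only, with less power than the stated 0.95.

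**Working it through.** **1. The plan's own sample size.** Inputs from the sample-size section: d = 0.5, power 0.95, alpha 0.05. Sidedness is not stated, and two-sided is assumed.

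n per arm = 2(z₀.₉₇₅ + z₀.₉₅)² / d² = 2(1.960 + 1.645)² / 0.25 ≈ 104, or 208 in total. The t-test version gives 104.93, so 105 per arm and 210 in total. A one-sided test would need only 87 per arm. The stated 106 per arm (212) is therefore reproduced closely, and its power is 0.952. Length of follow-up does not enter the formula.

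**2. The schedules side by side.**

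| Place in the protocol | Months from baseline | Months post intervention |
|---|---|---|
| Outcomes, HbA1c | 6, 12, 18, 24 | 6, 12 |
| Outcomes, weight | 12, 24 | 6, 12 |
| Outcome-measures table, HbA1c and weight rows | 6, 12, 18, 24 | 6, 12 |
| Study Intervention | 24 named | 6, 12 |
| Timing of Assessment Scales (psychometric and pain) | 6, 12, 18, 24 | not given |
| Project Management, Enrolled Nurse | 3, 6, 9, 12, 18, 24 | not given |
| Randomisation | 6, 12, 18 | 12, 24 |

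**3. Primary measurements affected.** Outcomes lists 6 times for HbA1c and 4 for weight, 10 in all. Read literally, the Randomisation bullet covers HbA1c at 6, 12, 18 and 12 post (4 of 6) and weight at 12 and 12 post (2 of 4). Not scheduled: 10 − 6 = 4, namely both outcomes at 24 months and at 6 months post.

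The bullet could also be read with its last two times counted from baseline. The 24-month visit then returns, 12 months is listed twice, and both post-intervention visits disappear. That again leaves 4 of 10 unscheduled, but a different four.

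**4. Minimum follow-up.** A participant followed for exactly 6 months supplies 1 of 6 HbA1c outcome points and 0 of 4 weight outcome points. The table does schedule weight at 6 and 18 months, so a 6-month weight would exist, but Outcomes does not list it as an outcome time.

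**5. Calendar.** Assume the stage months run from study start.

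| Enrolled in month | 24-month visit in month | Follow-up at month 24 | Follow-up at month 26 |
|---|---|---|---|
| 6 | 6 + 24 = 30 | 18 | 20 |
| 9 | 9 + 24 = 33 | 15 | 17 |

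The stated study length of 2.5 years is 30 months, so these visits fall at or beyond its end. After a full 24-month programme, the 12-month post visit of these recruits falls 36 months from enrolment, in months 42 to 45.

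**6. Illustrative power at 24 months.** The protocol does not say how many would be recruited late, so the share is an assumption. With d = 0.5 and a two-sided t-test at 0.05:

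| Share of each arm without a 24-month value | n per arm | Power |
|---|---|---|
| 0% | 106 | 0.95 |
| 10% | 95 | 0.93 |
| 20% | 85 | 0.90 |
| 30% | 74 | 0.86 |
| 40% | 64 | 0.80 |
| 50% | 53 | 0.72 |

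**The case against.** The strongest reply is that the Randomisation bullet is a single slip. Outcomes, the table, Study Intervention, the timing of the scales ("Psychometric and pain measurements will be taken at the same intervals; baseline, 6,12,18,24 months"), the consent text and the enrolled nurse's duties all include 24 months. Wherever post-intervention points are given elsewhere, they are at 6 and 12 months. The trial has one centre, named data-collection roles and a quarterly completeness review. This stands: a reader might infer that 24-month data will be lost, and the documents do not support that.

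The sample-size statement can also be defended. It is a planning floor, not an exit rule. Leaving the programme is not said to end data collection, and both arms are expected at a 24-month collection point. So one may not infer that participants are permitted to stop at 6 months. What remains is that the floor does not fit the outcome times it is meant to support.

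The 12-month remark is loose wording in a role description, and the same bullet sets data review at 0, 12 and 24 months. It is not a competing schedule.

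Finally, the Lead Academic and Population Health duties list analyses up to 6/2018, which suggests that follow-up was extended and the stage timeline not updated. That may explain the mismatch but does not remove it, because the protocol does not say which dates govern the final analysis.

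**Conclusion.** The inconsistency is real and lies in current, operative text. One bullet leaves 4 of the 10 primary outcome-by-time points unscheduled on a literal reading. The assumed minimum follow-up is shorter than either on-programme weight outcome time. The stage timeline gives recruits from months 6 to 9 at most 17 to 20 months of follow-up at month 26. The calendar result assumes that stage months count from study start, and the power figures assume the share missing.

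Three stronger readings are not supported:

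- That the primary comparison depends on 24 months alone. Outcomes lists several times and makes none decisive.
- That follow-up differs by arm. The rolling intake covers participants and controls alike.
- That the sample size is wrong. It reproduces.

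This is an internal inconsistency that should be fixed, not a flaw that invalidates the design.

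**What to change.** 1. Delete the schedule bullet in the Randomisation section and refer to the outcome-measures table as the only schedule.
2. In the sample-size section, replace the 6-month minimum with outcome collection to 24 months from baseline for all randomised participants in both arms who have not withdrawn consent, including those who leave the programme early.
3. Align Study Duration/Timelines and the 2.5-year statement so that the final analysis follows the last 24-month visit. Otherwise, state that later recruits contribute only to earlier time points and restate the power for 24 months.
4. Define the 6- and 12-month post-intervention points from the 24-month collection point in both arms, subject to the further consent described in Study Intervention. The programme lasts up to 24 months and only one arm attends it, so the end of the intervention is not a common reference date.
5. Correct the 12-month wording in the Population Health duties.

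Items 1, 4 and 5 are wording changes, and the visits are already in the table. Items 2 and 3 are more than wording. On the calendar above, the last 24-month visit is at about month 33, so the final analysis moves later. The post-intervention data run to about month 45 and depend on fresh consent.
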